# 13.4.5 Planned Supplemental Analyses for Primary Endpoint

To further assess the robustness of the results obtained from the primary analysis, a supplemental analysis is planned. We will conduct longitudinal modeling of the patientcompleted mRISRAS scores through 3-months post-radiation therapy. We anticipate that all patients will present with normal or near-normal skin based on the patient-completed mRISRAS score, corresponding to a baseline patient-completed mRISRAS score of < 4. The baseline patient-completed mRISRAS scores will be retained as part of the response vector. Furthermore, we will assume that the mean patient-completed mRISRAS scores in each arm are equal at baseline. Stated differently, the longitudinal model will include indicators for time (baseline being the reference level for time) and the interaction between arm and time, but no main effect of arm. The focus in this analysis will be on the interaction effect, which concerns arm comparisons of the patterns of changes in the mean patientcompleted mRISRAS scores. In addition to plotting the model-based mean response profiles by arm, we will report each time-specific comparison between arms with a 95% confidence interval. Because arm assignment is random, constraining the randomization arm means at baseline to be equal will, in general, be more powerful than including the arm main effect and making no assumptions about arm differences in the mean response at baseline. Also this modeling approach for adjusting for baseline incorporates all available data at baseline, and at subsequent post-baseline time points in the analysis, despite the fact that some patients may be missing baseline patient-completed mRISRAS scores. This would not be the case if we analyzed the post-baseline patient-completed mRISRAS scores

and made no adjustment for the baseline patient-completed mRISRAS scores by including it as a covariate.

To further assess the robustness of the results obtained from the longitudinal model, the following covariates will be included: the four stratification factors, and reconstructed breast size, separation, and modality of boost. Unstructured covariance will initially be used, though alternative covariance structures (e.g. compound covariance) will be investigated with the final covariance structure selected based on minimization of the Akaike information criterion.

# 13.5 Statement for Secondary Endpoints

# 13.5.1 Secondary Endpoints

There are six secondary endpoints:

- 1. Centralized, blinded provider-completed mRISRAS scores obtained from a blinded grading of the photographs taken at the end of radiation therapy.
- 2. The serially measured non-blinded institutional provider-completed mRISRAS scores obtained at baseline (i.e. prior to the start of radiation), during weekly radiation therapy, at  $10 (\pm 4)$  days post-radiation therapy, and at 3-months post-radiation therapy.
- 3. The serially measured combined patient- and provider-completed mRISRAS scores obtained at baseline (i.e. prior to the start of radiation), during weekly radiation therapy, at  $10 (\pm 4)$  days post-radiation therapy, and at 3-months post-radiation therapy.
- 4. Time to biopsy proven local and/or regional failure.
- 5. Acute adverse events.
- 6. Chronic radiation therapy-related adverse events including skin and soft tissue fibrosis, telangiectasia, and hyperpigmentation.

# 13.5.2 Analysis Plan for Secondary Endpoints

The first three secondary endpoints defined in Section 13.5.1 may provide supportive information about the prophylactic effect of the Mepitel Film on the primary endpoint. Stated differently, the first three secondary endpoints characterize prophylactic effects related to the primary endpoint but may extend our understanding of that effect. The collection of these three secondary endpoints constitutes a family of secondary endpoints. A gatekeeping statistical strategy will be used to control the Type I error rate at 0.05 across the primary and this secondary family of endpoints such that when an effect on the primary endpoint is demonstrated, this family of secondary endpoints will be examined and may contribute important supportive information about the effectiveness of the Mepitel Film.

A fixed-sequence strategy will be applied to this family of three secondary endpoints defined above. Provided the study's primary objective is achieved, a between-arm comparison will be made in the centralized, blinded provider-completed mRISRAS scores obtained from a blinded grading of the photographs taken at the end of radiation therapy. Notably, a panel of radiation oncology providers will perform the blinded, central review to grade the photographs. Each provider will independently score each photograph, and the average score will be calculated for each patient. The provider-completed mRISRAS score ranges from 0 to 24, obtained from summing the 4 individual scores, where higher scores correspond to increased radiation-induced skin reactions. For this first secondary endpoint,

our hypothesis is that the Mepitel Film arm will be associated with lower centralized, blinded provider-completed mRISRAS scores. To ensure that the researchers scoring the photographs are blinded to the prophylactic method that was applied, the mRISRAS scores will be based on photographs following the removal of the Mepitel Film for patients randomized to the Mepitel Film arm. Based on the published single-institution study, the expectation is that the centralized, blinded provider-completed mRISRAS scores recorded at the end of radiation therapy will be positively skewed. Therefore, the Wilcoxon ranksum test will be performed, and the methods of Hodges and Lehmann will be applied to compute a point estimate and confidence interval for the difference in medians between the two prophylactic methods. More specifically, patients will be ranked according to their centralized, blinded provider-completed mRISRAS scores recorded at the end of radiation therapy. The null hypothesis of no prophylactic effect is rejected, and the superiority of the Mepitel Film acknowledged, if in this ranking the 128 patients randomized to receive Mepitel Film rank sufficiently low. Under the null hypothesis (i.e. the distributions of both populations are equal), the probability that a centralized, blinded provider-completed mRISRAS score in the Mepitel Film arm is less than a centralized, blinded providercompleted mRISRAS score in the existing institutional standard of care arm is 0.5. Under the alternative hypothesis, we assume that this probability is 0.625. This probability corresponds to an effect size of 0.45 when the distribution is normal; based on the aforementioned largest single-institution study, the true but unknown effect size is likely to be considerably larger. With 192 patients (128 Mepitel Film; 64 existing institutional standard of care) and at a two-sided 5% significance level, the study will have at least 80% power to detect this shift in the population distributions, applying a two-sample Wilcoxon rank-sum test.

Provided that the first secondary endpoint achieves statistical significance at the 0.05 level, we will repeat the primary analysis defined in Section 13.4.2 based on the serially collected non-blinded institutional provider-completed mRISRAS scores. However, because a set of patients grouped within an institution are likely to respond similarly, we will also account for intra-institution correlation in the repeated-measures (means) mixed model with the inclusion of an institution random effect. Similarly, provided that the second secondary endpoint achieves statistical significance at the 0.05 level, we will repeat the above analysis based on the serially collected combined patient- and provider-completed mRISRAS scores. The combined patient- and provider-completed mRISRAS scores ranges from 0 to 36, obtained from summing the patient-completed and the provider-completed mRISRAS scores, where higher scores correspond to increased radiation-induced skin reactions. Based on the aforementioned largest single institutional study, we anticipate a prophylactic effect size > 0.5 for each of these two secondary endpoints; therefore, both secondary endpoints are adequately powered given the stated sample size in Section 13.3.

Within this family of secondary endpoints, all three secondary endpoints are important clinically; however, the pre-specified testing order of the three secondary endpoints was determined by the likelihood of success.

Physical exam to evaluate local and/or regional recurrence will occur every 3 months for years 1, and then every 6 months for years 2-5. Based on the natural history of breast cancer, the rates of local and/or regional recurrence are expected to be low, or around 1-5% at 24 months based on a recent meta-analysis of individual patient data for 8,135 women in 22 randomized trials furthermore, the estimated rates of local and/or regional recurrence are expected to be less than 10% by 60 months. To allow us to contextualize our study findings with those from this recent meta-analysis, another secondary endpoint is the time to biopsy proven local and/or regional failure, defined as the length of time from

the date of random assignment to the first instance of such an event; death will be treated as a competing event. A cumulative incidence function will be used to estimate the percentage of patients who experienced a local and/or regional failure within each arm at 6, 12, 24, 36, 48 and 60 months, treating death as a competing risk. Between-arm differences in the cumulative incidence functions will be tested for statistical significance using the procedure of Gray. Furthermore, a cumulative incidence function regression model of Fine and Gray will be used for multiple regression analyses; covariates included in the model will be the stratification factors and any potential confounding variables. Additionally, we will descriptively summarize the proportion of patients on each arm who experienced a locoregional recurrence by study month 60.

There are two other secondary endpoints that will be evaluated, and both are related to safety. The analysis of these safety endpoints will be based on the safety population, defined as all patients who initiated radiation; further the safety endpoints will be analyzed according to the intervention actually received. The constellation of acute and chronic adverse events (AEs) as scored using the National Cancer Institute Common Terminology Criteria for Adverse Events, v5.0 (CTCAE v5.0) will be summarized within arms by reporting the number and percentage of patients. Specifically, to evaluate the AE profiles associated with each arm, the maximum grade for each type of AE will be recorded for each patient and frequency tables will be reviewed to determine overall patterns. Additionally, the proportion of radiation dermatitis and skin and soft tissue fibrosis using NCI CTCAE v5.0 will be estimated within arms with the exact 95% confidence interval. Given the NCI CTCAE Version 5.0 scales for telangiectasia and hyperpigmentation are developed for total body surface area, they are not applicable to this study. As such, hyperpigmentation and telangiectasia will be evaluated on a 4-point scale, reflecting none, mild, moderate, and severe, and the corresponding number and percentage of patients reporting each will be presented according to arm. To evaluate the impact of chest wall separation on the constellation of AEs, we will display the AE profiles according to chest wall separation (> 25 cm; \le 25 cm) within each arm; additionally, other clinically meaningful separation thresholds will be explored depending on the distribution of the chest wall separation measurements.

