### 4.6 Stratification Factors

The randomization routine is found in Section 13.0 (Statistical Considerations). All eligible subjects will be stratified by:

- **4.6.1** Breast reconstruction (yes versus no)
- **4.6.2** Planned boost (yes versus no)
- **4.6.3** Planned bolus (yes versus no)
- **4.6.4** BMI <25.0 versus 25.0-29.99 versus  $\ge$  30.0

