Specifically, de-identified digital photographs obtained at baseline and following the completion of radiation (following removal of Mepitel for patients randomized to the Mepitel Film arm), will be viewed by a blinded panel of providers on a computer monitor. The degree of radiation dermatitis will be graded according to the mRISRAS (see Section 11.1.1, Section 13.4.2, and Section 13.5.2).

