#### 13.5.3 Planned Sensitivity Analyses for Secondary Endpoints

As a supportive analysis for the first secondary endpoint (centralized, blinded provider-completed mRISRAS scores), the van Elteren statistic, which is an extension to the Wilcoxon rank-sum test that accounts for the stratification factors, will be calculated.

A sensitivity analysis is planned for the second and third secondary endpoints in order to assess the robustness of the results in the presence of potential confounding variables such as reconstructed breast size, separation, and modality of boost. Further sensitivity analyses for the second and third secondary endpoints will comprise subgroup analyses to ascertain whether the effect of Mepitel Film remains clinically robust according to various categories of topical products (e.g. aqueous creams, petroleum ointments, etc.) used on the existing institutional standard of care arm.

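### The unadjusted Wilcoxon test that gates the secondary endpoints could be made more efficient by adjusting for the four factors used to balance randomisation

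*Combined protocol and SAP*

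**What the plan says.** - **Gating test (13.5.2).** The first of three fixed-sequence secondary endpoints is the panel's averaged blinded provider mRISRAS score at the end of radiation. Because skewness is expected, "Therefore, the Wilcoxon ranksum test will be performed", with a Hodges-Lehmann estimate and interval. Endpoints 2 and 3 are tested only if this test is significant at 0.05.
- **Planned power (13.5.2).** There are 128 and 64 patients. "Under the alternative hypothesis, we assume that this probability is 0.625", and "This probability corresponds to an effect size of 0.45 when the distribution is normal". The plan then states that "at a two-sided 5% significance level, the study will have at least 80% power to detect this shift in the population distributions".
- **Balancing factors (4.6, 13.1, 13.2).** "All eligible subjects will be stratified by" reconstruction, planned boost, planned bolus and three BMI classes. Assignment is by Pocock-Simon dynamic allocation, 2:1, with 10% of assignments going to the less balanced choice.
- **Adjustment elsewhere.** The primary mixed model includes the four factors (13.4.2). Endpoints 2 and 3 repeat that model with an institution random effect (13.5.2).
- **Stratified version (13.5.3).** The van Elteren statistic, "which is an extension to the Wilcoxon rank-sum test that accounts for the stratification factors", is planned for endpoint 1 as a supportive analysis only.
- **Baseline photographs (11.3).** The panel views and grades "de-identified digital photographs obtained at baseline and following the completion of radiation", but the analysis of endpoint 1 uses only the end-of-radiation score.

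**The concern.** Balancing the arms on prognostic factors makes the between-arm difference vary less from trial to trial. A test that ignores those factors still uses the full variance, so it rejects too rarely under the null and gives up power under the alternative. The plan itself treats the factors as relevant: section 1.3 links BMI, boost and bolus to skin dose or reaction severity, and section 13.2 justifies dynamic allocation by balance on prognostic factors.

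The first secondary endpoint is where this matters most. It is the only efficacy endpoint assessed blind, it has the lowest planned power in the confirmatory sequence, and a miss here stops formal testing of endpoints 2 and 3. It is also the only test in that sequence that leaves the factors out.

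**Working it through.** **1. Reproduce the plan's figure.** Inputs from 13.5.2: N = 192, share on film c = 2/3, P = 0.625, two-sided 5%. Noether's formula is power = Φ(√(12·N·c·(1−c))·|P−0.5| − 1.96).

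- √(12 × 192 × 2/9) = √512 = 22.63, and 22.63 × 0.125 = 2.828.
- Φ(2.828 − 1.960) = Φ(0.868) = 80.7%.
- N for 80% power is (1.960 + 0.842)² / (12 × 2/9 × 0.125²) = 188.4, so 189.
- Effect size: √2 × z(0.625) = 0.451, which matches 0.45.

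The stated power holds.

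**2. Closed-form effect of ignoring balanced factors.** Let R² be the share of score variance that the four factors explain. If balance is near complete, the true SD of the unadjusted statistic is about √(1−R²) of the value the test uses. Then:

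- true alpha ≈ 2Φ(−1.96/√(1−R²));
- unadjusted power ≈ Φ((2.828−1.96)/√(1−R²));
- adjusted power ≈ Φ(2.828/√(1−R²) − 1.96).

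At R² = 0.10, √0.90 = 0.949: alpha 3.9%, power 82.0% against 84.7%. At R² = 0.20, √0.80 = 0.894: alpha 2.8%, power 83.4% against 88.5%.

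**3. Simulation with the actual allocation.** 5,000 trials per setting, N = 192, 2:1 minimisation with a 90/10 coin, and a continuous latent score. Assumed: 40% reconstruction (13.6.2 expects 30-50%), 50% boost, 70% bolus, equal BMI thirds. R² is assumed throughout. Simulation error is about 0.3 points for alpha and 0.5 for power.

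| R² (assumed) | True alpha, Wilcoxon | True alpha, rank ANCOVA | Power, Wilcoxon | Power, rank ANCOVA | Power, van Elteren, 24 cells |
|---|---|---|---|---|---|
| 0 | 5.2% | 5.1% | 82.6% | 82.6% | 73.8% |
| 0.05 | 4.3% | 4.7% | 82.9% | 84.0% | 75.1% |
| 0.10 | 4.0% | 4.9% | 82.4% | 85.0% | 77.4% |
| 0.20 | 2.8% | 4.6% | 84.1% | 88.9% | 82.4% |
| 0.30 | 1.9% | 4.9% | 84.5% | 91.5% | 86.4% |

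A repeat simulation gave Wilcoxon alpha of 3.5%, 2.5% and 2.1% at R² 0.10, 0.20 and 0.30, and power of 82.5 against 85.1%, 82.1 against 87.4%, and 84.7 against 92.4%.

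**4. The planned stratified test.** The factors form 2 × 2 × 2 × 3 = 24 cells, so 192/24 = 8 patients per cell on average. At that sparsity van Elteren has less power than the unadjusted test up to R² = 0.20 and more only at 0.30.

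**5. Larger effects.** With P = Φ(d/√2), Noether power for the unadjusted test is 88% at d = 0.5, 96% at 0.6 and 99.8% at 0.8. The step 2 formulas at R² 0.10-0.20 put the gain from adjustment at 1.9-3.4 points at d = 0.5, 0.7-1.1 points at 0.6 and almost nothing at 0.8.

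**6. Baseline score.** A baseline score explaining a further 5% of variance added 1.3 points (86.0 to 87.3%, R² = 0.10) and 1.5 points (89.1 to 90.6%, R² = 0.20).

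**The case against.** The strongest reply is that nothing needs correcting. The power claim reproduces, type I error is not inflated, unadjusted power stayed above 80% in every setting tried, and a simple rank test backed by a stratified version is a recognised choice for a skewed score. All of this stands. A reader might infer that the endpoint is underpowered or its test invalid; the documents support neither.

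The size of the loss is also not in the documents. They call the factors prognostic but give no strength, so 10-20% is an assumption, and at R² = 0 nothing is lost. Section 13.5.2 further expects the true effect to be considerably larger than 0.45, and the gain shrinks to about 1 point or less at 0.6. Both limits stand.

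A reader might also infer that ignoring the graded baseline photographs is a substantial loss. That does not follow. Criterion 3.2.6 excludes active rash or pre-existing dermatitis in the field, and the baseline photographs precede radiation, so these scores should lie near zero. Baseline is not a balancing factor either, so leaving it out cannot make the test conservative.

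Finally, rank ANCOVA does not produce the Hodges-Lehmann estimate that the plan reports. That is a genuine cost, and the fix has to say what happens to the estimate.

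**Conclusion.** This is a cheap efficiency gain, not an error. The direction is firm: under this allocation, if the factors predict the blinded score, the unadjusted Wilcoxon test is conservative and weaker than an adjusted one. The size is conditional. With R² of 0.10-0.20 (assumed) and the planned effect of 0.45, the true two-sided error is about 2.5-4% and about 2-5 points of power are forgone. The loss is nil at R² = 0. The van Elteren test over 24 cells does not recover it in the range judged most relevant here, and could look weaker than the main result. The figures rest on a continuous simulated score and assumed factor prevalences.

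**What to change.** Before the blinded scores are linked to arm, amend 13.5.2 and 13.5.3 as follows.

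1. Name one gating test: a linear model on the ranks of the end-of-radiation blinded score, with arm and main effects of reconstruction, boost, bolus and BMI (three classes), and a two-sided 5% test of the arm term.
2. Keep the Hodges-Lehmann estimate and interval as the reported effect size, and the unadjusted Wilcoxon test as supportive.
3. Run the supportive van Elteren test on a pre-specified collapsed set of strata, not all 24 cells.
4. The blinded baseline grade may be added as a covariate; little gain should be expected.

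The present power statement can stay, since it is met without adjustment. No new data or patients are needed. There are two costs. The gating p-value and the Hodges-Lehmann interval come from different methods and may occasionally disagree, so the SAP should state that the p-value decides the gate. Rank ANCOVA also assumes additive covariate effects on ranks; its simulated type I error was 4.6-5.1% in the settings tabulated, and 4.4-5.5% once settings with a prognostic baseline score were included.

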Six secondary endpoints are included in this study. The first is designed to provide a centralized, blinded, provider-assessment of the maximum severity of radiation dermatitis as measured before and after radiation therapy using the provider-scored mRISRAS. Standardized views and photograph technique details may be found in Section 6.4 and Appendix III. The degree of radiation dermatitis as scored by the separate provider-scored component of the mRISRAS, and the combined patient- and provider- scored mRISRAS are included as additional secondary endpoints. These latter two endpoints will be based on the institutionally obtained data and will provide additional context to the primary and aforementioned blinded secondary endpoint. Time to biopsy proven local and/or regional failure will also be included as a secondary endpoint. The final two secondary endpoints include the analysis of acute and chronic toxicities according to CTCAE (Version 5.0). Because the CTCAE Version 5.0 scales for telangiectasia, and hyperpigmentation are developed for total body surface area, they are inappropriate for this study. Therefore, telangiectasia and hyperpigmentation will be scored using a 4-point scale representing none, mild, moderate, and severe. The CTCAE was selected when evaluating acute and chronic toxicities, as it is the most widely used tool by clinicians in reporting symptoms. Using this may allow for better cross-study comparisons with previously conducted clinical trials. In addition, PRO surveys do not always correlate with CTCAE toxicities, and the inclusion of both analysis tools will allow for a more robust analysis of the effect of Mepitel Film on the development of radiation dermatitis.

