Optional: Immediately following placement of the film, a warm blanket may be applied over Mepitel Film field and allowed to stay in place for 2-3 minutes. This may help with adherence and bring other unseen air bubbles to the surface.

Mepitel Film is typically applied using a patchwork approach. Based on the Mayo institutional experience, patients do not experience pain during application or removal of the Mepitel Film. If, after application of the Mepitel Film, the patient develops worsening pruritus or rash that, in the treating provider's opinion, is inconsistent with radiation related toxicity, and consistent with a film intolerance or allergy, the Mepitel Film may be removed. This is an unusual occurrence affecting less than 10% of patients, and typically happens within the first week following application. These patients should then be treated according to the institutional standard of care, and the film removal documented (see onstudy form in Medidata Rave). Should any patient develop pain secondary to film removal on this study, our recommendation is to proceed with conservative management with acetaminophen or ibuprofen as needed. If a patient develops moist desquamation under the Mepitel Film, the area of film immediately overlying the affected area of skin may be removed, and the treating provider should direct treatment of the moist desquamation according to their institutional standard of care. Mepitel Film should not be reapplied to

this area; however, it should remain in place over the remainder of the skin that is not affected by moist desquamation.

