Based on the aforementioned single-institution study, the distribution of the combined patient-and provider-completed mRISRAS scores (averaged over the post-randomization assessments) were positively skewed. As such, we propose using the AUC to summarize the sequence of repeated patient-completed mRISRAS scores for each patient. This summary measure tends to be approximately normally distributed. We hypothesize that the Mepitel Film arm will be associated with an improved AUC summary measure, corresponding to decreased patient-completed mRISRAS scores compared with institutional standard of care. With 192 patients randomized in a 2:1 ratio (128 Mepitel Film; 64 existing institutional standard of care), the study will have at least 90% power for a two-sample t-test to detect an effect size of -0.5 (Mepitel Film vs institutional standard of care) based on the AUC summary measure with a two-tailed alternative and a 5% Type I error rate. These results assume that two sequential tests are made using the O'Brien-Fleming spending function (see Section 13.4.3).

We anticipate that up to 10% of patients will not have met the eligibility criteria and/or not have submitted any mRISRAS data, and thus the target sample size will be inflated to 216 patients (144 Mepitel Film; 72 existing institutional standard of care). Importantly, any placement of the Mepitel Film will make the patient evaluable for the primary analysis provided that the patient had at least one patient-completed mRISRAS score, and was randomized (See Section 13.4.2 and the definition of the full analysis set).

Using conservative estimates, based on the Alliance Community Interest and Feasibility Survey conducted in May of 2018, we anticipate an accrual rate of 9 patients per month; therefore, to achieve the targeted accrual of 216 patients we anticipate that the accrual period will be approximately 24 months. Since the last protocol scheduled follow-up visit is 60 months post-radiation therapy, the corresponding total study duration will be approximately 84 months.

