To determine the frequency and severity of patient-reported itching, radiation skin reaction, pain, and breast swelling and tenderness, as measured by the PRO-CTCAE, the maximum grade for each of these events will be recorded for each patient and frequency tables will be generated. The descriptive analysis of the PRO-CTCAE endpoints will be based on the

safety population, defined as all patients who initiated radiation; further the safety endpoints will be analyzed according to the intervention actually received.

To determine the long-term severity of radiation dermatitis, the serially measured combined patient- and provider-completed mRISRAS scores obtained at 6-months, 1-year, and 2-years post-radiation therapy, will be descriptively summarized within each arm. These analyses are intended to complement and further contextualize the analyses related to chronic skin toxicity.

Lastly, descriptive summaries of the response items captured by the Thin Film Clinical Utilization Survey (Appendix VIII) will be tabulated for the patients who receive the Mepitel Film.

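### CTCAE and PRO-CTCAE skin outcomes are summarised only by intervention received, with no definition for removed film and no summary by randomised arm

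*Combined protocol and SAP*

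**What the plan says.** Section 13.5.2 treats acute and chronic adverse events (secondary endpoints 5 and 6) as safety endpoints. On the population: "The analysis of these safety endpoints will be based on the safety population, defined as all patients who initiated radiation". On the grouping: "further the safety endpoints will be analyzed according to the intervention actually received". The same paragraph says that "the proportion of radiation dermatitis and skin and soft tissue fibrosis using NCI CTCAE v5.0 will be estimated within arms", with exact 95% intervals, and it tabulates telangiectasia and hyperpigmentation by arm on a four-point scale. Section 13.6.2 applies the same population and grouping to PRO-CTCAE itching, radiation skin reaction, pain, and breast swelling and tenderness. No between-arm test or contrast is planned for any of these, and no version by randomised arm.

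Two other places use the CTCAE skin outcomes to judge benefit. Section 1.5 says that having both CTCAE and patient-reported tools "will allow for a more robust analysis of the effect of Mepitel Film on the development of radiation dermatitis". Section 13.9 assumes 10% versus 45% for CTCAE events in the African American and Hispanic subgroup, gives a 90% interval for the difference, and treats its lower limit as clinically important. It does not name the analysis population; its group sizes of 36 and 18 come from the randomisation ratio.

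The film instructions in Section 7.2.2 allow removal for itch or rash judged to be film intolerance or allergy, expected in fewer than 10% of patients. They continue: "These patients should then be treated according to the institutional standard of care". Film over moist desquamation may also be removed locally. In the Appendix I pilot, 4 of 33 patients stopped film: two for pruritus, one for non-adherence and one for an unrelated rash.

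The nearest thing to an exposure definition is in Section 13.3: "any placement of the Mepitel Film will make the patient evaluable for the primary analysis". That concerns evaluability for the primary endpoint and does not define treatment received for the safety tables.

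**The concern.** Grouping by treatment received is usual for harms of a device. Here the same tables also carry the outcomes that the device should prevent. Pruritus is at once a solicited adverse event, a PRO-CTCAE item, a recognised film effect (Section 9.2) and a reason for taking the film off. If a patient whose film is removed is counted as standard of care, membership of the groups depends on something that happened after randomisation and is related to the outcome.

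The plan does not settle how such a patient is classed. It also speaks of results within arms while grouping by what was received, so two analysts could build different tables from the same data. Descriptive percentages with exact intervals will be read side by side as supporting or contradicting the primary result. They should not be able to move because of a classification left open until the data are seen.

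**Working it through.** **The plan's own figure.** The only design figure for the CTCAE skin outcomes is the Section 13.9 interval, with 45% of 18 (standard of care) against 10% of 36 (film). The unpooled normal interval is 0.35 ± 1.645 × √(0.45 × 0.55/18 + 0.10 × 0.90/36) = 0.35 ± 1.645 × √0.01625 = 0.35 ± 0.210, that is 0.14 to 0.56. This agrees with the plan. The width is 0.419 here and at most 0.421 over the stated 45%–70% range, so 0.42 also holds. No stated figure is wrong.

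**Inputs for the regrouping check.**
- Arm sizes 128 and 64 (Section 13.3).
- Share of film patients moved, f: 10% (the ceiling implied by Section 7.2.2) and 4/33 = 12.1% (Appendix I), with 5% for scale.
- Overall risk 45% in both arms, so the film does nothing. The 45% is borrowed from the standard-of-care rate in Section 13.9.
- Movers' risk r: 45%, 70% or 90%. The documents give no value, so these are assumptions.

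**Formulas.** Patients who keep the film have risk s = (0.45 − f·r)/(1 − f), which holds the randomised film arm at 45%. If movers are classed as standard of care, that group's risk is c = (64 × 0.45 + 128·f·r)/(64 + 128·f). The apparent benefit is c − s; the true difference is zero.

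**Example, f = 10%, r = 70%.** s = (0.45 − 0.07)/0.90 = 0.422. c = (28.8 + 12.8 × 0.70)/76.8 = 37.76/76.8 = 0.492. The apparent benefit is 0.069.

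| f | r | Film, as received | Standard of care, as received | Apparent benefit (points) |
|---|---|---|---|---|
| 5% | 70% | 43.7% | 47.3% | 3.6 |
| 5% | 90% | 42.6% | 49.1% | 6.5 |
| 10% | 45% | 45.0% | 45.0% | 0 |
| 10% | 70% | 42.2% | 49.2% | 6.9 |
| 10% | 90% | 40.0% | 52.5% | 12.5 |
| 12.1% | 45% | 45.0% | 45.0% | 0 |
| 12.1% | 70% | 41.6% | 49.9% | 8.3 |
| 12.1% | 90% | 38.8% | 53.8% | 15.0 |

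**If the film works.** Take randomised rates of 10% and 45% (true difference 35 points) and f = 10%. The as-received difference is 29.2 points for r = 10%, 34.7 for r = 30% and 45.8 for r = 70%. The error can go either way.

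**If any placement counts as film received.** Patients whose film is removed stay in the film group and removals cause no shift. What remains is film never applied and film used in the control arm. The plan gives no rate for either.

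**The case against.** The strongest case against is that these are safety analyses and the plan labels them so. Objectives 2.2.1 to 2.2.3 ask whether the film prevents dermatitis; objectives 2.2.5, 2.2.6 and 2.3.4 ask only about frequency and severity. Grade 3+ radiation dermatitis is part of the accrual-suspension rule in Section 13.8.3, so it is monitored as a possible harm. The summaries are descriptive and lie outside the gatekept family of the first three secondary endpoints. That is correct, and it limits how much this point matters. It does not remove the benefit reading that Sections 1.5 and 13.9 place on CTCAE.

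Three stronger readings are tempting and should not be drawn.

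- A reader might infer that the trial's randomised comparison of dermatitis is broken. It is not. The primary endpoint is analysed by randomised arm (Section 13.4.2), the second and third secondary endpoints repeat that analysis, and the blinded photograph endpoint is described in terms of patients randomised to film (Section 13.5.2).
- A reader might infer that film-caused itch would be charged to the control arm and reverse the sign of the pruritus result. That requires a patient who wore the film, reacted and had it removed to be classed as never having received it. Section 7.2.2 describes later skin care and does not assign an analysis group, and Section 9.2 lets events be attributed to the film. In the pilot 2 of 33 stopped for pruritus, which is about 8 of 128.
- A reader might infer that control-arm film use adds materially to the problem. Section 7.2.1 prohibits prophylactic barrier films in that arm, and no rate of use is given. Random, complete crossover would in any case dilute the randomised contrast; it would not show selection bias in the as-received one.

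**Conclusion.** The point holds as a gap in descriptive analyses. Outcomes that the plan partly uses to judge benefit are summarised only by treatment received, and that term is undefined for a patient whose film is removed early, removed in part or never applied. If removed-film patients are classed as standard of care, a film with no effect could show a benefit of about 7–8 points (movers' risk 70%) or 12.5–15 points (movers' risk 90%) when 10–12% are moved. The shift is zero if movers have average risk and the film has no effect.

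These sizes rest on assumed movers' risks, on a 45% rate that the plan states for a subgroup, and on removal rates at or slightly above the plan's own ceiling; the 12.1% comes from a proton-therapy pilot and covers all reasons for stopping. No controlled test, stated power or stated interval changes. The change is worth making because it is cheap and settles the classification before the data are seen.

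**What to change.** 1. In Sections 13.5.2 and 13.6.2, add summaries by randomised arm for CTCAE radiation dermatitis and fibrosis, telangiectasia, hyperpigmentation and the PRO-CTCAE skin items. Give each a between-arm difference with a confidence interval, at a grade threshold fixed in advance.
2. Keep the as-received safety tables as planned, and state that any film placement counts as having received film, so that patients whose film is later removed stay in the film group. Patients assigned to film who never had it applied are then covered by the summaries in item 1.
3. In Section 13.9, name the as-randomised population for the subgroup proportions and their difference.

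The cost is some SAP wording and a few extra tables, using a grouping variable already held. No new data are needed, and the primary analysis and the gatekeeping sequence stay as they are.
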